## 6 Methods

[figure not shown]
### 6.1 Treatment

#### 6.1.1 Identity of Investigational Product – N/A

#### 6.1.2 Dosage, Administration, Schedule

Visit 1 will consist of informed consent and enrollment. The study will begin with a 1 to 3 -week baseline period for insulin optimization. At visit 2, participants will be randomized for either the very low carbohydrate diet or standard carbohydrate diet that they will follow for 2 weeks. At visit 2 (virtual/telephone/in person), participants will be instructed on how to keep diet journal and report relative amounts of food during the 24-hour recall phone calls. After 2 weeks on the first diet, participants will come to the HRU/CSRU/Masonicare for Visit 3, the hyperinsulinemic euglycemic-hypoglycemic clamp. Following this visit, the participants will have a 1-3 week washout period. At Visit 4 (virtual/telephone/in person), the next diet will be reviewed. They will follow that diet for 2 weeks and then return to the HRU/CSRU/Masonicare for Visit 5 and the second hyperinsulinemic euglycemic-hypoglycemic clamp. After this visit, the study will be complete.

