## Primary Outcome Variables

### Aim 1:

Primary Efficacy Outcome: Percent time spent in the target range of 70-180 mg/dL during 2 weeks on each diet.

Secondary Safety Outcomes: We will measure the percent time spent in the hypoglycemic (<54 mg/dL, <70 mg/dL) and hyperglycemic (>180 mg/dL, >250 mg/dL) ranges. We will also measure the average sensor glucose values, standard deviation, and coefficient of variation during each 2-week diet period. We will compare the proportion of days with elevated fasting beta-hydroxybutyrate levels ( $\geq 0.6$  mmol/L) during each diet period. Number of episodes of diabetic ketoacidosis and severe hypoglycemic events during each period (baseline, diet periods, and washout period) will also be reported.

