9. For females of reproductive potential: use of highly effective contraception for at least 1 month prior to screening and agreement to use such a method during study participation and for an additional 4 weeks after the end of the dietary intervention.
10. For males of reproductive potential: use of condoms or other methods to ensure effective contraception with partner

An individual who meets any of the following criteria will be excluded from participation in this study:

1. Current use of glucose-lowering agents other than insulin
2. Unstable psychiatric disorders, including eating disorders (DSM-V criteria).
3. Weight loss medications within the last 6 months
4. Pregnancy or lactation, or planning pregnancy within the next 6 months
5. BMI < 19 kg/m^2 for individuals 18 years of age or older

6. BMI < 5%ile for individuals under 18 years
7. Weight less than 49 kg or 108 pounds (due to blood draw)
8. Other medical conditions that may interfere with glucose metabolism and insulin sensitivity (as determined by the investigator).

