#### 6.2.4 Pharmacokinetics (if applicable) – N/A

#### 6.2.5 Biomarkers (if applicable) – N/A

### 6.3 Study Procedures

6.3.1 **Study Schedule:** See figure 1. The study will consist of 5 visits: The enrollment visit, randomization, and 2 visits for clamp procedures following each diet and a virtual/telephone follow up visit.

Enrollment Visit 1	Screening and Consent. Discuss research procedures. Meet with a registered dietitian or trained research staff to discuss diet and education on keeping a diet record. Review of insulin pump and CGM data.
Randomization Visit 2 (Virtual/Telephone or in person)	Randomization will occur, as will discussion of subsequent diet (and how to obtain meals), study requirements, and next steps. Review of insulin pump and CGM data.
Clamp Visit 3	Hyperinsulinemic-euglycemic 2-step clamp followed by hypoglycemic clamp. Study questionnaires. Review insulin pump and CGM data. Discussion of washout period and next steps. Review of insulin pump and CGM data
Visit 4 (Virtual/Telephone or in person)	Discussion of subsequent diet (and how to obtain meals), study requirements, and next steps. Review of insulin pump and CGM data.
Clamp Visit 5	Hyperinsulinemic-euglycemic 2 step clamp followed by hypoglycemic clamp. Study questionnaires. Review of insulin pump and CGM data. Discussion of potential need for insulin dose changes and follow up.
Visit 6	Interviews will be conducted over the telephone or over zoom.

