**Follow Up Calls:**

- Participants will be followed up weekly to make insulin dose adjustments during the insulin optimization and washout periods. Insulin pump and CGM information will be reviewed during these phone calls.
- Participants will also be screened for any symptoms that may be related to very low carbohydrate diets on a weekly basis or more often as needed (symptoms including nausea, vomiting, abdominal pain, constipation, fatigue, and lightheadedness). If these occur, participants will be instructed to ensure adequate caloric intake is achieved and hydration is maintained.

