**Visit 4 (virtual/telephone or in person):**

- Anthropomorphic measures (weight, % body fat, % muscle mass, % water, % bone) – at home or on scale in office
- Insulin pumps and CGMs will be downloaded to assess glycemic control. The diabetes treatment regimen will be adjusted as clinically indicated.
  - If participants are starting the very low carbohydrate diet, insulin doses will be reduced by 10-20%, as clinically indicated, to prevent hypoglycemia.
- Second diet will be assigned.

- If participants are starting the very low carbohydrate diet, meals can be picked up 2-3 times per week at the metabolic kitchen located at Yale New Haven Hospital by study participants or by research staff. Research staff will work with participants to deliver the meals if they are unable to pick them up.
- If we are unable to acquire meals from the metabolic kitchen, we will use a mail order meal service that provides information about macronutrient content of all meals provided that meet the standards of the dietary measures.
- Participants will be instructed to check daily fasting blood ketone levels.
- Participants will receive dietary instruction and review the dietary requirements of the study. Participants will be instructed to keep a dietary record (MyFitnessPal application, written, and/or with photos) for the duration of the dietary period.
- Participants will be instructed to call the pediatric diabetes emergency line (available 24/7) in any case of severe low blood sugar, elevated ketone levels, or symptoms of ketosis. Participants will also receive education on the treatment of hypoglycemia, we will ensure that all participants have glucagon at home.
- Participants will be contacted 3 times per week (2 scheduled, 1 unscheduled) for a 24-hour dietary recall. During these telephone follow up calls, food diary will be reviewed, ketone levels reviewed, and CGM data will be uploaded and reviewed.
- Prior to the HRU/CSRU/Masonicare admission, we will recommend a standard diet be given and no food be eaten after 12am (except for in cases of hypoglycemia). A snack will be recommended at 9pm the evening prior to the clamp. Participants will be advised to limit exercise in the 3 days prior to study to limit acute effects of recent exercise on insulin sensitivity.

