### 6.3.6 End of Study and Follow-up

- Participants will be instructed to contact study staff and make them aware of any adverse events that occur during the study (severe hypoglycemia, diabetic ketoacidosis, etc). Information about adverse events will also be asked at each study follow up visit.
- Upon completion of the clamp procedures, participants will be instructed to monitor their glucose levels carefully and contact clinic staff if they note that

insulin adjustments are needed. Follow up appointments with a diabetes care provider will be recommended within 2 weeks of the end of the study. Their primary diabetes provider will also be contacted and made aware that they have completed the study.

- If participants withdraw from the study early, participants will be instructed to monitor their glucose levels carefully and contact clinic staff if they note that insulin adjustments are needed. Follow up appointments with a diabetes care provider will be recommended within 2 weeks of ending the study. Their primary diabetes provider will also be contacted and made aware that they have withdrawn from the study.
- Diabetes providers will be made aware of any adverse events that take place during the study or information that is considered medically necessary for their overall health. Participants will be made aware of any information that may be shared with their diabetes provider. There is no plan to share results with the primary diabetes providers unless something pertinent to their diabetes management occurs during the study.

**6.3.7 Removal of subjects:** Participants may be withdrawn if they are unable to follow the dietary requirements and study procedures, including keeping a diet journal, testing ketone levels, and wearing a CGM at least 75% of the time.

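### No dated, study-collected safety follow-up is defined after the second clamp, so the period after leaving the very low carbohydrate diet is observed systematically in only one of the two sequences

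*Combined protocol and SAP*

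**What the plan says.** Section 6.1.2 treats the ends of the two diet periods differently. After the first clamp (Visit 3), "Following this visit, the participants will have a 1-3 week washout period". After the second (Visit 5), "After this visit, the study will be complete".

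Section 6.3.5 (Follow Up Calls) sets the contact between diets: "Participants will be followed up weekly to make insulin dose adjustments during the insulin optimization and washout periods". Pump and CGM data are reviewed on those calls.

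The Synopsis (Aim 1) says that the number of DKA episodes and "severe hypoglycemic events during each period (baseline, diet periods, and washout period) will also be reported". Sections 5.2.1 and 6.2.1 list the same periods, and Section 6.5.1 compares the counts by period with a Poisson mixed model.

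Insulin changes with the diet. When the very low carbohydrate diet starts, "insulin doses will be reduced by 10-20%, as clinically indicated, to prevent hypoglycemia" (Visit 4; the same at Visit 2).

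The plan is not silent about what follows Visit 5:
- Section 6.3.5 (Visits 3 and 5) has pumps and CGMs downloaded at the clamp visit and the regimen adjusted as needed.
- Section 6.3.6 says that after the clamps "participants will be instructed to monitor their glucose levels carefully and contact clinic staff if they note that" their insulin needs changing. It also recommends a diabetes-care appointment within 2 weeks, has the primary diabetes provider told, and has adverse events asked about at each study follow-up visit.
- Section 6.3.1 lists a Visit 6 with this content: "Interviews will be conducted over the telephone or over zoom". It has no date.

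**The concern.** Coming off the very low carbohydrate diet changes both diet and insulin needs, and Section 3.2.1 names changes in diet or insulin dose as a possible cause of glycemic deterioration. Section 3.1 presents short-term safety as an open question that the trial should help to answer. Events soon after leaving the diet are therefore part of its safety picture.

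Under the plan, those events are collected systematically or not according to the randomised sequence. Where they are collected, they are filed under washout together with events in participants who have just left the standard diet, and no split by preceding diet is stated. A reader of the results could not say how often DKA or severe hypoglycemia followed the end of the test diet. A count of zero would rest on half the participants.

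**Working it through.** **Numbers per sequence.** Section 6.4.2 gives 16 evaluable participants (paired t-test, effect size 0.75, two-sided alpha 0.05, 80% power) and 20 enrolled after 20% attrition. Both figures reproduce: power at n = 16 from the noncentral t with 15 degrees of freedom is 0.8006, 16 is the smallest n that reaches 80%, and 16 / (1 - 0.20) = 20. Section 6.1.3 aims for equal sequences, so there are 10 per sequence if all 20 count and 8 if 16 do. The present point changes none of these figures.

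**The two exits side by side.**

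| After leaving the very low carbohydrate diet | Diet taken first | Diet taken second |
|---|---|---|
| Place in the schedule | Washout, 1-3 weeks (6.1.2) | After the stated end of study (6.1.2) |
| Regimen review at the clamp | Yes, Visit 3 (6.3.5) | Yes, Visit 5 (6.3.5) |
| Scheduled study contact afterwards | Weekly calls (6.3.5) | Visit 6 interview only, undated (6.3.1, 6.3.5) |
| Period in which DKA and severe hypoglycemia are counted | Washout (Synopsis, 5.2.1, 6.2.1) | None named |

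**Scheduled observation.** Person-weeks = participants x weeks of washout.
- Diet first: 10 x 1 = 10 to 10 x 3 = 30 (8 to 24 with 8 participants).
- Diet second: 0 scheduled.

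**Pooling.** All 20 participants have a washout, so the washout period holds 20 x 1 = 20 to 20 x 3 = 60 person-weeks. If washout lengths are alike in the two sequences, half follows each diet.

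**What a zero count would exclude.** With no events in n participants, the exact one-sided 95% upper bound on per-participant risk is 1 - 0.05^(1/n).
- n = 10: 1 - 0.05^(1/10) = 25.9%; n = 20: 1 - 0.05^(1/20) = 13.9%.
- With attrition, n = 8: 31.2%; n = 16: 17.1%.

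**Does Visit 6 close the gap?** Section 6.3.6 has adverse events asked about at follow-up visits, and Visit 6 could be one. The documents do not settle it. Section 6.1.2 ends the study at Visit 5. Section 6.3.1 announces five visits but tabulates six. The recruitment text in Section 6.3.3 speaks of six. Section 5.3 allows people who have already finished to be contacted for the interview. The Visit 6 content in Section 6.3.5 is the interview alone. Even if the question is asked at Visit 6, there is no window to define the period covered and no reporting period to hold the answer.

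**The case against.** The strongest reply is that the plan hands participants over to usual care in an orderly way. Staff review devices and can adjust the regimen at Visit 5, participants are told what to watch for, an appointment within 2 weeks is recommended, and the provider is informed. Section 3.2.1 also asks participants to report late adverse effects, although under the catheter risk. An adverse-event question at Visit 6 may already be intended.

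Much of this stands. A reader might infer that safety follow-up stops outright at the second clamp, and these provisions show that it does not. They are clinical care or participant-initiated reports, however, apart from Visit 6, whose timing and safety content are undefined.

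Other stronger readings also lack support:
- A reader might infer that the trial could find no DKA or severe hypoglycemia on the diet because nobody looked. During the diet, every participant in both sequences has daily fasting ketone checks and contact three times a week, and events are counted in both diet periods.
- A reader might add the 2 weeks of the second diet and set 3-5 weeks of follow-up against none. Events in those weeks belong to the second diet period, so the comparable interval is the 1-3 week washout.
- A reader might take the contraception criterion, "agreement to use such a method during study participation and for an additional 4 weeks after the end of the dietary intervention", as a recognised risk window after the diet. It is an eligibility rule for females of reproductive potential, and nothing links it to ketosis or insulin change.
- A reader might put the step back at 200 / 75 = 2.7 times the carbohydrate. Those are approximate intakes on the study diets. The washout diet and habitual intake are not stated.

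**Conclusion.** The point holds as a gap in safety data collection and reporting. After the second clamp there is no dated study safety contact and no period in which DKA or severe hypoglycemia is counted. Systematic data on leaving the very low carbohydrate diet therefore come from about half the participants, 10-30 person-weeks against 0, and are pooled with exits from the standard diet.

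This assumes equal sequences, participants leaving the diet when the clamp ends the period, and, for the upper bounds, a common per-participant risk over windows of similar length. If Visit 6 is meant to include the adverse-event question, the gap narrows to its missing date and missing reporting period.

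On-diet safety counts and the within-participant comparison of time in range are unaffected.

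**What to change.** 1. Reconcile Section 6.1.2 (complete after Visit 5) with Visit 6 in Sections 6.3.1 and 6.3.5 and with the adverse-event question in Section 6.3.6, and state when a participant's adverse-event collection ends.
2. Give Visit 6 a date window, for example one matching the washout length, and list an explicit query for adverse events, DKA and severe hypoglycemia since Visit 5.
3. Add a post-diet-2 period to the DKA and severe hypoglycemia outcomes in the Synopsis and Sections 5.2.1, 6.2.1 and 6.5.1.
4. Report washout and post-diet-2 events by the diet just left.

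The cost is a few questions at a contact already planned, some changes of wording, and slightly longer participation on paper. The sample size does not change. Any insulin or monitoring schedule after Visit 5 is for the investigators to decide.

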**Figure 1. Schedule of visits during the study.**

#### 6.1.3 Method of Assignment/Randomization

Block randomization will be used to ensure an equal number of participants complete diets in each of the specified sequences.

#### 6.1.4 Blinding and Procedures for Unblinding – N/A

#### 6.1.5 Packaging/Labelling

There is no study drug for this protocol. However, stable isotopes will be obtained from Cambridge Isotopes, Cambridge, MA), which is routinely audited internally by its QA department and externally by customers, notified bodies, and regulatory

agencies (e.g. FDA). Isotopes will be stored in the Investigational Pharmacy and will be prepared before the subjects undergo tests. Deuterated water will also be obtained from Cambridge Isotope Labs.

#### **6.1.6 Storage Conditions**

The glycerol and glucose isotopes, dextrose, and insulin infusions will be kept with Yale-New Haven Hospital Investigational Drug Service (IDS), which will keep all documentation. The IDS will prepare preparations of isotopes before each study and store it in the med room in the YCCI. Pyrogen and sterility are tested and documented by Cambridge Isotopes before shipping to us.

#### **6.1.7 Concomitant therapy**

As is stated in the exclusion criteria, no medications (other than insulin) that cause glucose lowering will be permitted during the study.

#### **6.1.8 Restrictions- N/A**

### **6.2 Assessments**

#### **6.2.1 Efficacy**

Aim 1	
Primary Efficacy Outcome	Percent time spent in the target range of 70-180 mg/dL during 2 weeks on each diet, as measured by CGM.
Secondary Safety Outcomes	We will measure the percent time spent in the hypoglycemic (<54 mg/dL, <70 mg/dL) and hyperglycemic (>180 mg/dL, >250 mg/dL) ranges. We will also measure the average sensor glucose values, standard deviation, and coefficient of variation during each 2-week diet period. We will compare the average fasting $\beta$ -hydroxybutyrate levels during each diet period. Number of episodes of diabetic ketoacidosis and severe hypoglycemic events during each period (baseline, diet periods, and washout period) will also be reported.
Aim 2	
Primary Safety Outcomes	Mean levels of glucagon produced in response to hypoglycemia after each diet will be measured using a 2-step hyperinsulinemic euglycemic-hypoglycemic clamp. These will be measured every 15-30 minutes of during the first step of the euglycemic clamp and every 15 minutes during the hypoglycemic clamp.
Secondary Safety Outcomes	Measure mean levels of other counterregulatory hormones (cortisol, epinephrine, norepinephrine) and $\beta$ -hydroxybutyrate that are produced in response to hypoglycemia during the clamp will be compared after each diet period. Fasting levels of glucagon, free fatty acids, $\beta$ -hydroxybutyrate and IGF-1 (measure of growth hormone secretion) prior to the clamp will be compared after each diet period.
Secondary Efficacy Outcomes	Hepatic glucose production and adipose tissue lipolysis will be measured using stable isotope infusions during the euglycemic and hypoglycemic portions of the clamp. We will compare differences in hepatic glucose production during each clamp between a standard and very low carbohydrate diet.

Aim 3	
Primary Safety Outcome	We will measure hypoglycemia awareness symptoms after 20-30 minutes of euglycemia and hypoglycemia during each clamp using a validated Edinburgh Hypoglycemia Symptom questionnaire. Scores during euglycemia will be compared to scores during hypoglycemia for each clamp. Scores during hypoglycemia after each diet period will also be compared.
Primary Efficacy Outcome	To describe how participants feel about and react to following a very low carbohydrate diet, interviews will be conducted over zoom (HIPAA compliant). Data will be coded and emerging patterns will be combined into descriptive themes.

### 6.2.2 Safety and Pregnancy-related policy

- Women of childbearing age will have a urine pregnancy test performed at the time of the screening/enrollment visit and the need for contraception for the entire duration of the study will be discussed. Additional urine pregnancy tests will take place the morning prior to each clamp visit (visit 3 and visit 5).
- Hematocrit levels will be tested prior to the clamp procedures (visit 3 and visit 5). Samples will be obtained with the minimum necessary blood volume. The point of care YSI glucose determinations require only 0.3 ml of blood per measurement. We will ensure that blood volume obtained does not exceed a maximum of 5cc/kg in pediatric participants and 550 ml in adult participants
- Continuous glucose monitoring data will be reviewed twice per week (or more frequently as needed) to ensure participants are wearing the devices and to monitor for hyperglycemia and hypoglycemia. Insulin doses will be titrated by trained research staff based on clinical care standards to ensure safety by minimizing hypo- and hyperglycemia.
- Daily fasting blood ketone checks will be performed during the study intervention and as needed for symptoms of ketosis. If ketones are elevated, participants will be instructed to call the diabetes emergency line 24/7 for further instruction. All patients in our clinics are instructed to call this number if they develop elevated ketones at home. These values will also be reviewed 3 times per week when 24-hour dietary recall is performed.

### 6.2.3 Adverse Events Definition and Reporting

#### Definitions

Adverse event (AE) means any untoward medical occurrence associated with the use of an intervention in humans, whether or not considered intervention-related (21 CFR 312.32 (a)).

An AE or suspected adverse reaction is considered "serious" (SAE) if, in the view of either the investigator or sponsor, it results in any of the following outcomes:

- death,
- a life-threatening adverse event,
- inpatient hospitalization or prolongation of existing hospitalization,
- a persistent or significant incapacity or substantial disruption of the ability to conduct normal life functions,
- a congenital anomaly/birth defect, or

- An important medical event that may not result in death, be life-threatening, or require hospitalization may be considered serious when, based upon appropriate medical judgment, they may jeopardize the participant and may require medical or surgical intervention to prevent one of the outcomes listed in this definition. Examples of such medical events include allergic bronchospasm requiring intensive treatment in an emergency room or at home, blood dyscrasias or convulsions that do not result in inpatient hospitalization, or the development of drug dependency or drug abuse.

